- 3.2.8 Pregnant women are excluded from this study because imatinib mesylate is an agent with the potential for teratogenic or abortifacient effects. Because there is an unknown but potential risk for adverse events in nursing infants secondary to treatment of the mother with imatinib mesylate, breastfeeding should be discontinued if the mother is treated with imatinib mesylate.
- 3.2.9 HIV-positive patients on combination antiretroviral therapy are ineligible because of the potential for pharmacokinetic interactions with imatinib mesylate and the possibility of associated severe immunosuppression.
- 3.2.10 Patients with active hepatitis C or hepatitis B infection as defined by seropositivity for hepatitis C or hepatitis B (HepBSAg) and elevated transaminases, as GVHD manifestations involving the liver will be indistinguishable and drug-toxicity uninterpretable.
- 3.2.11 Persistent malignancy, requiring ongoing therapy.

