6 DOSING DELAYS/DOSE MODIFICATIONS

Treatment modifications: All dose modifications must be discussed with the PI or LAI. This study will utilize version 4.0 of the NCI Common Terminology Criteria for Adverse Events (CTCAE) (<http://ctep.cancer.gov/reporting/ctc.html>) for toxicity and adverse event reporting.

Only those adverse events deemed possibly, probably, or definitely related to imatinib mesylate will be used in the definition of DLT. Events that are considered disease related will not be considered dose limiting. Expected pre-existing or concurrent manifestations of cGVHD or systemic steroid therapy may include the following examples: fatigue, colitis, cushingoid appearance, anorexia, xerostomia, nausea, taste alteration, arthritis, fibrosis, myositis, osteonecrosis, osteopenia, dry eye, watery eye, pain, dyspnea, vaginal dryness, skin atrophy, alopecia, hyperpigmentation, skin dryness, hypopigmentation, nail changes, photosensitivity, pruritus, rash, and ulcers. Any of the above symptoms newly presenting after initiation of imatinib mesylate must be carefully evaluated for attribution, i.e. new skin rash will be biopsied to determine drug reaction versus GVHD.

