
Gastrointestinal-Upper GI
 
 • Early satiety OR • Anorexia OR • Nausea & Vomiting 
Gastrointestinal-Esophageal
 
 • Dysphagia OR • Odynophagia 
Gastrointestinal-Lower GI
 
 • Diarrhea 
Lungs
 
 • Bronchiolitis Obliterans 	
0= no symptoms 1=mild, occasional symptoms, with little reduction in oral intake during the past week 2=moderate, intermittent symptoms, with some reduction in oral intake during the past week 3=more severe or persistent symptoms throughout the day, with marked reduction in oral intake, on almost every day of the past week
 
0= no esophageal symptoms 1=Occasional dysphagia or odynophagia with solid food or pills during the past week 2=Intermittent dysphagia or odynophagia with solid foods or pills, but not for liquids or soft foods, during the past week 3=Dysphagia or odynophagia for almost all oral intake, on almost every day of the past week
 
0= no loose or liquid stools during the past week 1= occasional loose or liquid stools, on some days during the past week 2=intermittent loose or liquid stools throughout the day, on almost every day of the past week, without requiring intervention to prevent or correct volume depletion 3=voluminous diarrhea on almost every day of the past week, requiring intervention to prevent or correct volume depletion
 
Pulmonary Function Tests with Diffusing Capacity (attach report for person > 5 yrs old) FEV-1
 
% Predicted
 
Single Breath DLCO (adjusted for hemoglobin)
 
% Predicted
						

Health Care Provider Global Ratings: In your opinion, do you think that this patient's chronic GVHD is mild, moderate or severe? 0=none 1=mild 2=moderate 3=severe
	
Where would you rate the severity of this patient's chronic GVHD symptoms on the following scale, where 0 is cGVHD symptoms that are not at all severe and 10 is the most severe cGVHD symptoms possible:
 
0 1 2 3 4 5 6 7 8 9 10
 
cGVHD symptoms not at all severe
 
Most severe cGVHD symptoms possible
						

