	Trial 1	Trial 2	Trial 3	Average	% of Predicted
R					
L					

4) Walk Velocity:

Total Distance Walked in 2 Minutes _____ feet walked in 2 minutes, giving him/her velocity _____. % of predicted _____

5) HAP: _____ AAS _____

Version date: 04/20/15

MRN:

AAROM:

Cervical spine:

Flexion	Extension	R SB	L SB	R Rotation	L Rotation

Shoulders:

	Abduction	Flexion	IR	ER
R				
L				

Elbows:

	Extension	Flexion
R		
L		

Wrists:

	Extension	Flexion
R		
L		

Hips:

	IR	ER
R		
L		

Knees:

	Extension	Flexion
R		
L		

Ankles:

	ADF	APF
R		
L		

Signature

Printed Name

Date

30 Appendix O: Lung Function Score

The Lung function score (LFS) is computed by the extent of FEV₁ and DLCO compromise (>80% = 1, 70 – 79% = 2, 60 – 69% = 3, 50 – 59% = 4, 40 – 49% = 5, <40% = 6). The scores for FEV₁ and DLCO are then added together, and the sum is reduced to an overall category according to the following table.

Category	30.1.1 Lung function	30.1.2 LF score
I	Normal	2
II	Mild decrease	3 – 5
III	Moderate decrease	6 – 9
IV	Severe decrease	10 – 12

It is important to emphasize that LFS has never been used in chronic GVHD response assessments and its exact role in this setting needs to be determined. To allow validation in trials absolute values of both FEV₁ and DLCO are recorded on the data collection forms.

31 Appendix P: Scoring of non-ScGVHD cGVHD manifestations

1. Skin GVHD (Dermatology): Total skin score (Appendix E)
2. Oral GVHD (Dental): Total mouth score (Appendix E)
3. Ophthalmologic GVHD (Ophthalmology): Response based on determination of bilateral Schirmer's Test (without topical anesthesia >9 y/o, with topical anesthesia <9 years old.)
4. Bronchiolitis obliterans (PFTs): Measure of absolute FEV1 and lung function score (Appendix O). BO response will be measured by standard pulmonary function tests. Patients will be evaluated by complete PFT's (with and without bronchodilators) and baseline will be the best measured FEV1. Percent change is based on the relative change as compared to baseline. PFT testing variability is typically <10% and a 20% change is thought to be significant.
5. Liver GVHD: Laboratory values: ALT, AST, total bilirubin, alkaline phosphatase.
6. Gastrointestinal GVHD: Gastrointestinal symptom score (Appendix E).

Progression (PD): defined as at least one of the following:

Organ and Starting Score or Value	Progression Criterion
Skin (% of BSA)	$e - s \geq 25$
Eye (mm Schirmer's test)	$s - e \geq 5$ mm
Mouth (Schubert Scale 0-15)	$e - s \geq 3$

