Hematology 3 Platelet count 4 Eosinophil count 5 ≥ 3 X ULN • < 3 X ULN	$s - e \geq 50,000/\mu\text{L}$ and $e < \text{LLN}$ $e - s \geq 3$ X ULN $e - s \geq 2$ X ULN
Gastrointestinal (0 -3 scales)	$e - s \geq 1$
Liver function (ALT, alkaline phosphatase and bilirubin) 6 $s \geq 3$ X ULN 7 $s < 3$ X ULN	$e - s \geq 3$ X ULN $e - s \geq 2$ X ULN
Lungs (Lung function scale 12 points)²	$e - s \geq 3$
Other	> 1 steroid pulse per 3 month period

Abbreviation: s: starting score or value; e: ending score or value; ULN: upper limit of normal; LLN: lower limit of normal. If the starting lung function score is ≥ 10 , progression is defined as $\geq 5\%$ decrease of FEV₁ in two tests measured at least 2 weeks apart.

Partial Response (PR): defined as at least one of the following:

Organ and Starting Score or Value at Baseline	Partial Response Criterion¹
Skin (% of BSA) 8 > 50 9 25-50 10 < 25	$e/s \leq 0.5$ and $e > 0$ $s - e \geq 25$ and $e > 0$ Only CR; no PR possible
Eye (mm Schirmer's test) 11 < 5 mm 12 5-10 mm	$e - s \geq 5$ mm and $e < \text{LLN}$ Only CR; no PR possible
Mouth (Schubert Scale 0-15) 13 > 8 14 4-7 15 < 4	$e/s \leq 0.5$ and $e > 0$ $s - e \geq 4$ and $e > 0$ Only CR; no PR possible
Hematology 16 Platelet count 17 Eosinophil count 18 $\geq 3 \times \text{ULN}$ 19 $< 3 \times \text{ULN}$	$e - s \geq 100,000/\mu\text{L}$ and $e < \text{LLN}$ $e/s \leq 0.5$ and $e > \text{ULN}$ Only CR; no PR possible
Gastrointestinal (0 -3 scales) 20 3 21 2 22 1	$e = 1$ or 2 $e = 1$ Only CR; no PR possible
Liver function (ALT, alkaline phosphatase and bilirubin) 23 $\geq 3 \times \text{ULN}$ 24 $< 3 \times \text{ULN}$	$e/s \leq 0.5$ and $e > \text{ULN}$ Only CR; no PR possible
Other	Stable disease in the face of weaning steroid.

Abbreviations. s: starting score or value; e: ending score or value; ULN: upper limit of normal; LLN: lower limit of normal

Complete Response (CR): defined as at least one of the following

1. Skin: >90% reduction of baseline involvement.
2. Ophthalmologic: Return to normal Schirmer's score in both eyes.
3. Oral: Resolution of oral mucosal involvement.
4. BO: PFT: improvement in FEV1 > 0.70.
5. Liver: Normalization of laboratory values of transaminases and bilirubin.
6. GI: (Upper GI) Absence of symptoms of nausea, dysphagia, vomiting, and odynophagia and stable weight. (Lower GI) Absence of diarrhea and stable weight.

32 Appendix Q: Patient Instructions

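### Appendix P calls GI cGVHD progression on a 1-point symptom rise with no attribution condition, so mild imatinib side effects can count as both toxicity and worsening GVHD

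*Combined protocol and SAP*

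**What the plan says.** **Scoring (Appendix E, clinician form).** Upper GI is a single item covering early satiety, anorexia, and nausea and vomiting. A score of 1 is "1=mild, occasional symptoms, with little reduction in oral intake during the past week". Diarrhea is a separate item, where a score of 1 is "1= occasional loose or liquid stools, on some days during the past week". Neither item asks about cause. Platelet count and liver tests are entered as measured.

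**Use as organ response (Appendix P).** The inputs are named as disease: "Gastrointestinal GVHD: Gastrointestinal symptom score (Appendix E") and "Liver GVHD: Laboratory values: ALT, AST, total bilirubin, alkaline phosphatase". The rule then reads "Progression (PD): defined as at least one of the following". In the row "Gastrointestinal (0 -3 scales") the criterion is a rise of at least 1.

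**Expected toxicity (Section 8.1).** Nausea, vomiting and diarrhea are in the likely (>20%) column. Anorexia, oral mucositis, platelet decrease, and increases in ALT, AST, alkaline phosphatase and bilirubin are in the less likely (<=20%) column.

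**Where the plan does consider cause.**
- Section 6 lists symptoms that may come from cGVHD or steroids, among them nausea, anorexia, colitis, rash and ulcers. It requires an attribution review when any of them is new on imatinib, and gives as its example that "new skin rash will be biopsied to determine drug reaction versus GVHD".
- Section 3.2.10 excludes active hepatitis because "GVHD manifestations involving the liver will be indistinguishable and drug-toxicity uninterpretable".
- Appendix F requires drug effect to be excluded for some marked items when cGVHD is diagnosed.

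**The concern.** Evaluating the response of other organs is a stated secondary objective (Section 1.2). With one arm and no control, nothing in the design separates a drug effect on the gut from GVHD of the gut, so the scoring rule would have to do it. As written it does not. New mild nausea on imatinib moves the upper GI score from 0 to 1, and that alone is organ progression.

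The same nausea is collected as toxicity. The patient calendar lists nausea, vomiting and diarrhea as side effects and grades nausea by ability to eat and drink, which is close to the oral-intake scale in Appendix E. Appendix B has these diaries reviewed for toxicity. The GI organ result and the GI toxicity result would then be partly the same data, and the organ result would lean against imatinib.

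**Working it through.** The plan gives no sample size, power or error rate for Appendix P progression, so there is no figure to reproduce. The point rests on the definitions; the arithmetic only shows scale.

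**Step 1. How large a change does each criterion need?**

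| Appendix P criterion | Change that counts as progression | Matching imatinib effect in Section 8.1 |
|---|---|---|
| GI | rise of at least 1 on a 0-3 scale | nausea, vomiting, diarrhea (>20%); anorexia (<=20%) |
| Mouth | rise of at least 3 on a 0-15 scale | oral mucositis (<=20%) |
| Platelets | fall of at least 50,000/µL, ending below the lower limit of normal | platelet decrease (<=20%) |
| Liver | rise of at least 2 x ULN (start below 3 x ULN) or at least 3 x ULN (start at or above it) | ALT, alkaline phosphatase, bilirubin increase (<=20%) |

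Only the GI criterion pairs a minimal change with a common drug effect.

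**Step 2. Does an existing safeguard reach Appendix P?**
- The Section 6 review covers new nausea, anorexia, ulcers and rash. It serves the definition of dose-limiting toxicity and is not linked to Appendix E or P. Its list does not name vomiting or diarrhea.
- The Appendix F exclusion of drug effect concerns diagnosis. It marks mouth ulcers, among others, but not anorexia, nausea, vomiting or diarrhea.
- Appendix P asks for a second test only for lung function with a starting score of 10 or more. By contrast, Section 12.1.2 requires two consecutive evaluations for ROM progression and counts steroid pulses only if given for ScGVHD.

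No safeguard conditions the GI criterion on cause.

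**Step 3. Illustrative size.** Take two GI items (upper GI; diarrhea) and assume each has a 20% chance of a drug-related rise. The 20% is the lower edge of the likely class in Section 8.1.
- Full overlap: 20%, or 0.20 x 10 = 2.0 of 10 evaluable patients.
- Independent: 1 - 0.8² = 1 - 0.64 = 36%, or 3.6 of 10.

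For a general per-patient chance p (assumed), with 10 patients:

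| p | expected false GI progressions, 10p | chance of at least one, 1 - (1 - p)^10 |
|---|---|---|
| 0.05 | 0.5 | 40% |
| 0.10 | 1.0 | 65% |
| 0.20 | 2.0 | 89% |
| 0.36 | 3.6 | 99% |

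The 20% input is probably too high. Section 8.1 pools 5169 patients from other uses, while this cohort takes 100-200 mg and Appendix E asks only about the past week at three-monthly visits. The one low-dose reference in the plan is the 100-200 mg pilot described in Section 2.3. It reports minor non-hematologic toxicity in 4 of 15 patients (27%), but not which types, so it cannot be turned into a GI rate.

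**The case against.** The case on the other side has several parts.

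- **The endpoint is limited.** Section 12.1 keeps other organs out of response scoring, and Section 14.4 makes all secondary endpoints exploratory. This stands. A reader might infer that drug nausea could count as study progression or affect the primary result. The documents do not support that: Section 12.1.2 defines progression by ROM or steroid pulses, and no section links Appendix P progression to removal (Section 5.3) or to time to progression (Section 14.4).
- **Attribution is not ignored.** A reader might infer that the plan sees the overlap only for rash and liver. Section 6 goes further and covers new nausea, anorexia and ulcers. That stands, but the review does not feed Appendix P.
- **Some patients may not be scored.** Section 12.1 speaks of other involved organs. If that means involved at baseline, a patient without GI GVHD who develops nausea may not be counted. This could shrink the problem. It does not remove it, because drug symptoms can also raise a score that starts above zero, though such patients need further worsening.
- **The consensus criteria may deal with cause.** Section 2.2 bases response assessment on NIH consensus criteria. Their content cannot be checked from these documents, and Appendix P as written carries no such rule.
- **As-observed scoring is conservative.** In an open-label, single-arm study, removing worsening on the investigator's own attribution would shift results toward imatinib. This stands, and is why the as-observed score should not be replaced.

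**Conclusion.** The point holds for GI, within an exploratory secondary objective. Followed literally, Appendix P can classify mild imatinib-related nausea, vomiting, anorexia or diarrhea as GI GVHD progression while the same event is recorded as toxicity. Mouth, platelet and liver lack the same condition but need larger changes, so it would be wrong to say that a small change in any of these organs is enough.

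The size is illustrative only: 20% to 36% of patients open to a false GI progression if each of two GI items carries a 20% chance of a drug-related rise, and probably less here. A reader might treat nausea, vomiting and diarrhea as three independent 20% risks and reach 1 - 0.8³ = 49%. Appendix E does not support that, because nausea and vomiting share one upper GI item. The illustration also assumes that every patient is scored for GI and has room for the score to rise.

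**What to change.** Leave the Appendix P criteria and the as-observed score as the main version. Add a sentence to Appendix P, or to Section 14.4, saying that any organ worsening also recorded as an adverse event with probable or definite attribution to imatinib (Section 8.2) is flagged, and that organ progression is reported both with and without the flagged changes. Apply it to all organs, since the gap is common to them, and state the number flagged for GI separately.

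The cost is one sentence and one table column. Section 8.2 already defines the attribution categories, and Section 8.4 requires all adverse events in routine data, so mild events should be available even though Section 7.2.2 leaves Grade 1 out of the IRB summary. Someone must match the date of the adverse event to the week covered by the score. The drawback is that attribution is an unblinded judgement that could favour imatinib, which is why both versions are shown and neither replaces the other.

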5 TREATMENT PLAN

5.1 Imatinib Mesylate Administration

This is an open-label pilot study of oral imatinib mesylate for ScGVHD. Adult patients will receive 100 mg imatinib mesylate daily and pediatric patients will be dosed at 65 mg/m² daily (100 mg maximum) for 28 days. If tolerated, after 28 days, adult patients will be increased to 200 mg daily and pediatric patients will be increased to 130 mg/m² (200 mg maximum). If the 100mg (or 65mg/m²) dose is not tolerated due to unacceptable toxicity within the first 28 days despite following the dosing delay guidelines (section 6.0), the drug will be discontinued, except for patients taking 100mg daily who are also on potent CYP3A4 inhibitors. This group will be allowed dose reduction to 50mg. Children with a BSA < 0.97 (starting dose 50mg) who do not tolerate the drug during the first 28 days will be taken off study because dose reduction below 50mg is not possible with the 100mg tablets. Treatment cycles are continuous 28-day cycles with no rest period between cycles.

Imatinib mesylate is supplied as 100 mg tablets. Adult patients will initially receive 100 mg imatinib mesylate daily and pediatric patients will be dosed at 65 mg/m² daily (100 mg maximum, see nomogram below). After 1 month, adult patients will increase to 200 mg daily and pediatric patients will receive 130 mg/m² daily. Individual patient dosages will be rounded to the nearest 50 mg increment. Tablets are scored and the 100 mg tablets may be cut into achieve 50 mg dosing. According to the package insert, tablets may be dispersed in a glass of water or apple juice, stir until disintegrated and administer immediately. Since no long-term stability data are available, the administration of imatinib suspension should not be delayed. Patient should take drug with a meal and a large glass of water (patients who dissolve their tablets in liquid do not need to drink additional water). See Appendix Q for patient instructions.

The product labeling for imatinib mesylate provides dosing guidelines for patients with renal dysfunction, as defined by the following criteria (Prod Info GLEEVEC® oral tablets, 2010):

Renal Dysfunction Definitions (based on Product labeling)

Mild CrCL = 40-59 mL/min

Moderate CrCL = 20-39 mL/min

Severe CrCL = <20 mL/min

Mild renal dysfunction

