10.2 Special Studies

10.2.1 MRI imaging of sclerotic cGVHD ([name], CC/DRD)

Objective: To establish the role of MRI in the detection of sclerotic skin changes in patients with cGVHD.

Rationale: Development of objective imaging evaluations will aid better diagnosis, staging, subclassification and clinical response assessment in cGVHD.

Methods: Contrast enhanced MRI of muscle and fascia will be performed in cGVHD patients. The MRI will gather information about anatomic disease extent and depth, and investigate features of disease on enhanced imaging that may potentially reflect disease activity. An affected joint under evaluation as a primary endpoint for range of motion evaluation will be preferentially imaged in a 1.5 or 3.0 Tesla clinical MRI unit, with the aid of a surface coil. Scans will encompass a representative region of cutaneous/subcutaneous disease, and will include: STIR, T1 spin echo, and 3D field echo scan. After intravenous injection of a standard, weight-adjusted dose of an FDA approved gadolinium chelate (0.1mmol/kg), high resolution post contrast field echo scans will be obtained. Additional, higher resolution imaging may be performed at 3T using a microscopy coil adapted for detailed assessment of skin and subcutis in selected cGVHD patients. Non-FDA approved MRI sequences may be performed on these patients under protocol 87C0091, PI: [name].

Scoring: MR findings will be scored for the following anatomic areas, with respect to the listed features:

1. Skin: thickening, edema
2. Subcut tissue: septal thickening, compartment narrowing, edema
3. Deep fascia: edema, thickening
4. Muscle: edema
5. Epimysium: edema

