12 MEASUREMENT OF EFFECT

12.1 Response Criteria

The primary endpoint for evaluation of response is established at the 6-month time point. Patients will be evaluated for response based on their ScGVHD evaluation. For the secondary endpoints, other involved organs will be evaluated, but not used in scoring for response to therapy (see appendix P).

12.1.1 ScGVHD will be measured and scored at baseline and every three months from beginning protocol treatment and will be measured by Physiatry. The ROM score will be

based on the composite joint ROM from the three most affected joints for patients with 3 or more affected joints (Appendix M, N). For those patients with fewer than 3 affected joints, the 2 most affected joints or the change in the overall ROM if only a single joint is affected. As there is not currently standardized assessment for ScGVHD, in our experience ROM assessments provide the most reproducible measure of disease progression or improvement in patients with involvement of skin and subcutaneous tissue involving joints. ROM will be measured using the American Academy of Orthopaedic Surgeons Criteria (AAOS, Chicago 1965). Percent change is based on percent change of deficit as compared to baseline. This scoring system has been successfully used in several recently published studies from the NCI evaluating the effects of anti-fibrotic agents on radiation-induced fibrosis[36,37].

As mentioned above, range of motion has been used in other clinical trials as a primary outcome measure, including trials conducted at the NIH Clinical Center studying pentoxifylline [37] and pirfenidone [36] for the treatment of radiation-induced fibrosis. There are several criteria by which ROM may be performed. Our physiatrist will perform the ROM measurements using the American Academy of Orthopaedic Surgeons Criteria (AAOS), which has been used extensively for several decades. However, reproducibility is a potential concern, and we will attempt to minimize this by the use of a single clinician who is experienced in ROM measurement. It is also important to recognize that there are no alternative validated measures of skin fibrosis in ScGVHD [32]. This emphasizes the value of the secondary objective to “establish outcome criteria for the evaluation of ScGVHD using multi-modality objective and subjective assessments, including magnetic resonance imaging, skin scoring, and patient self-reported measures”.

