Patients may drop out due to disease progression, recurrent malignancy, inability to comply with study requirements, unacceptable toxicity, or need for additional systemic therapy for cGVHD, prior to the 6-month evaluation. It is expected that this will be the case in no more than 10-20 percent of patients. In order to allow for this, up to 13 patients will be permitted to be enrolled, but accrual will stop when 10 are evaluable. Patients will only be replaced if they are not evaluable for the ROM evaluation at the 3 month time point for any reason, since this would make the slope estimate impossible to determine (in the absence of intermediate time points, which are not useful to obtain since anti-fibrotic responses are likely to be slow and thus not reflective of any benefit when possible to be identified).

There could be bias due to drop out because of progression, but this is expected to be very limited. In addition to 6-month values, the trial will also obtain intermediate values at 3 months. By having these intermediate values available, estimates from fitting a regression line or from a

'last observation carried forward' technique may be used to try to obtain reasonable substitutes for values not available from those who do not complete 6 months of observation. This type of procedure will be done with appropriate caveats if implemented.

A stopping rule based on the appearance of unresolved grade 3 or any grade 4 toxicity attributable to imatinib will be as follows: if at any time during the trial, a cumulative total of 2 patients experience this level of toxicity, no further patients will be enrolled. This is because the upper one-sided 80% confidence bound on fractions between 2 of 3 and 2 of 10 patients with toxicity extends from 0.38 to 0.93, and as such, this level of toxicity would be consistent with levels clearly considered excessive and which outweigh the potential benefit of the agent in this population.

As this is a one-arm pilot study, there is no control for natural history or regression to the mean, but improvements without the use of treatment are unlikely since this manifestation of GVHD is typically static or progressive and does not remit or improve spontaneously. Nonetheless, if results from this trial look promising, then a randomized study is indicated as the next evaluation.

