From Lee et al. BBMT, 8:444-452, 2002 [38]

28 Appendix M: Functional Assessment: ROM, Walk Test, Grip Strength, Function Scales

Description:

There are standard ranges for all tests. Every joint has an established range of motion (ROM). For example, the normal ROM for shoulder flexion is 180 degrees, each quartile is 45 degrees. If the shoulder can be put through 125 degrees it is 75% of normal. Similar is for grip strength (in Kg or pounds of pressure) and for walk time. The velocity is established based on norms for age and sex. For example if 18 feet/second, if divided by 4 and gets quartiles.

The HAP has a standard scoring mechanism which determines normal activity. However, it has not been looked at with respect to disability. We have done this internally for several studies based on internal agreement. The maximum activity score (based on 94 questions) was divided into performance groups: top quartile are normal performers with scores of >81; next quartile with scores of 73-81; next quartile 61-72 and bottom quartile 60 and below.

ROM:

Active-assisted range of joint motion serves as very useful objective measure of chronic GVHD tissue response in patients whose large joints or trunk are involved by sclerotic skin changes. Norms are available for adults and for children more than 3 years of age.

Patients will be examined by a physiatrist upon enrollment and every 3 months while on study. Exam will consist of active-assisted ROM performed on all major joints. Based on the level of impairment (current degree/normal degree) and the clinical assessment (level of sclerotic tissue changes) the physiatrist will choose three signal joints (1-2 for patients with fewer involved joints) to be measured for primary endpoint evaluation. Physiatrist will determine percent change in impairment and record for all involved joints.

Version date: 04/20/15

29 Appendix N: Physiatry Evaluation ROM Assessment:

Patient Name _____ MRN _____ Date _____

1) Active Assisted ROM Assess if patient ≥ 4

	Actual Number	% of Predicted	Impairment Assessment			
			Normal=0	Mild=1	Moderate=2	Severe=3
Joint 1						
Joint 2						
Joint 3						

2) Other Musculoskeletal Findings

	Normal=0	Mild=1	Moderate=2	Severe=3
Grip Strength Assess if patient ≥ 6	0-25% ()	26-50% ()	51-75% ()	>75% ()
Walk velocity Assess if patient ≥ 6	0-25% ()	26-50% ()	51-75% ()	>75% ()
HAP Assess if patient ≥ 16	>81 ()	73-81 ()	61-72 ()	<61 ()

3) Grip Strength of the Dominant Hand

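### Appendix M has one unmasked physiatrist measure ROM, choose the endpoint joints and derive percent change, in a one-arm trial where any examiner expectation reads as drug effect

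*Combined protocol and SAP*

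**What the plan says.** Section 5.1 sets the design: "This is an open-label pilot study of oral imatinib mesylate for ScGVHD". Section 14.1 states one of its limits: "As this is a one-arm pilot study, there is no control for natural history or regression to the mean". The same section makes the 6-month change in ROM the primary endpoint and tests it with a paired t-test (signed rank if the data are not normal), planned on 10 evaluable patients.

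Appendix M describes the measurement. The schedule is given first: "Patients will be examined by a physiatrist upon enrollment and every 3 months while on study". The technique is then specified in a separate sentence: "Exam will consist of active-assisted ROM performed on all major joints". Using the degree of impairment together with a clinical assessment, "the physiatrist will choose three signal joints (1-2 for patients with fewer involved joints) to be measured for primary endpoint evaluation". The paragraph ends: "Physiatrist will determine percent change in impairment and record for all involved joints".

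Section 12.1.1 recognises that reproducibility may be a problem and answers: "we will attempt to minimize this by the use of a single clinician who is experienced in ROM measurement".

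Appendix N, the recording form, has fields for the actual number, the percent of predicted and an impairment grade for three joints, and then degrees per motion. It has no field for percent change and no column for earlier visits.

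Sections 11.1, 12.1 and 14.1 and Appendices M and N describe no masked or second ROM reader, no withholding of earlier values from the examiner, and no derivation of percent change by someone else.

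**The concern.** In active-assisted ROM the examiner helps the movement, so the degrees reached depend partly on the examiner. Appendix M calls the measure objective but describes no safeguard for an examiner who knows the treatment and has earlier values to hand.

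Using one experienced clinician reduces variation between examiners. It does not deal with that clinician's own expectation, and it puts every reading in one person's hands. If expectation moves the joints of a patient in the same direction, averaging over three joints does not remove it.

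A concurrent control arm would share a common shift; a one-arm test against zero has nothing to subtract it from. Section 14.1 discusses natural history, regression to the mean and drop-out bias, but not the assessor. It also says that a promising result would lead to a randomized study, so an avoidable upward bias could affect that decision.

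**Working it through.** **1. Access to baseline values.** Appendix M assigns percent change to the physiatrist. Percent change is a function of the baseline and current values, so the physiatrist must have the baseline values at some point. The sentence gives no timing. Whether the calculation is done during the exam or afterwards is open, and the layout of Appendix N does not show that earlier values are in view while measuring. The finding needs only that the person who measures also derives the change.

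**2. The plan's own power figure.** Inputs from 14.1: n = 10, two-sided alpha 0.05, change of 1.0 SD, stated power 80%. For a paired t-test the statistic follows a noncentral t distribution with 9 degrees of freedom and noncentrality d × √n = 1.0 × √10 = 3.162; the critical value is 2.262. Power = 80.3%, so the stated figure reproduces. The smallest observed mean change that reaches significance is 2.262/√10 = 0.72 SD.

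**3. Same test, no drug effect, systematic examiner shift.** The documents give neither the size of such a shift nor the SD of ROM change. Both are assumed here: shift 2 to 5 degrees, SD 8 to 15 degrees. Set d = shift/SD and use the same formula.

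| Assumed shift | Assumed SD | d | d × √10 | Two-sided rejection |
|---|---|---|---|---|
| 0 | any | 0 | 0 | 5.0% |
| 2° | 15° | 0.133 | 0.42 | 6.7% |
| 2° | 8° | 0.250 | 0.79 | 10.9% |
| 5° | 15° | 0.333 | 1.05 | 15.7% |
| 5° | 8° | 0.625 | 1.98 | 42.3% |

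The calculation is in degrees for simplicity, whereas the endpoint is a percent change. The rates describe the whole assumed shift, whatever its source.

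**4. A 5-degree shift against the 25% response cut.** Inputs: normal shoulder flexion of 180 degrees (Appendix M), minimum eligible deficit of 25% (3.1.2), response as an increase of more than 25% (12.1.3). Baseline ROM = 0.75 × 180 = 135 degrees; deficit = 45 degrees.

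- Deficit scale (12.1.1): the cut is 0.25 × 45 = 11.25 degrees, and 5/11.25 = 44%.
- Absolute-ROM scale (14.1): the cut is 0.25 × 135 = 33.75 degrees, and 5/33.75 = 15%.

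The share on the deficit scale falls as the deficit grows. At a 90-degree deficit the cut is 22.5 degrees and 5 degrees is 22% of it. Sections 12.1.1 and 14.1 use different denominators and need to be reconciled, but both rest on the same readings.

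**The case against.** The strongest reply is that the plan is a pilot which already limits its claims and standardises the measurement. It uses published orthopaedic criteria and one experienced examiner, admits the lack of a control, and names a randomized trial as the next step. Appendix N is already close to the form one would want, since it asks for current degrees and shows no earlier values. Hiding old numbers also leaves the main source of expectation in place, because the examiner knows that every patient is taking the drug. All of this stands. It limits what the fix can achieve, but it is no reason for the assessor to derive the endpoint.

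Three stronger readings are tempting and are not supported.

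- A reader might infer that percent change is worked out at the exam with the baseline sheet in hand. Appendix M gives no timing, and Appendix N has no place for that figure.
- A reader might infer that examiner shift alone decides who stays on treatment. Section 12.1.2 requires ROM progression on two consecutive evaluations 2 to 4 weeks apart, so one reading cannot remove a patient on that ground. The 6-month response under 12.1.3 carries no such confirmation and does bear on continuation under 5.3, but nothing shows that expectation would change any particular decision.
- A reader might extend the point to MRI scoring in 10.2.1. The plan is silent on the order of reading there, silence does not show unmasked reading, and MRI is an exploratory secondary measure. It forms no part of this point.

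**Conclusion.** The point holds as a limited design weakness. Appendix M puts measurement, joint selection and derivation of change in the hands of one unmasked assessor. The design has no control to absorb a systematic shift, and the only stated safeguard addresses a different problem.

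The size cannot be established from the documents. The 7% to 42% range follows entirely from assumed shifts and SDs, and its low end is little above the nominal 5%. It should not be read as the inflation caused by the Appendix M sentence, or as what the fix would remove: it is total examiner shift, of which access to earlier values is an unknown part. Likewise, 44% of the response cut applies only on the deficit scale, for one shoulder at the minimum deficit; on the absolute-ROM scale of 14.1 it is 15%. The case for acting is that the change is cheap and removes one avoidable route for bias.

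**What to change.** Replace the last sentence of the ROM paragraph in Appendix M with a procedure on these lines:

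- The signal joints are named at baseline and kept for all later visits.
- At each visit the physiatrist records degrees per motion on a fresh Appendix N sheet that names the signal joints, without access to earlier values.
- After the sheet is signed, a named member of the existing study staff (coordinator or statistician) computes percent change.
- That person promptly tells the principal investigator of any result meeting the progression threshold, so that the 2-to-4-week confirmation in 12.1.2 is kept.

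In 14.1, next to the caveat on regression to the mean, add that the ROM examiner knew that all patients were on open-label treatment and that expectation could have affected the readings.

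The cost is a change of wording and of form handling, with no added visits. The documents give the calculation to nobody but the physiatrist, so someone must be named and available at each visit. The physiatrist loses sight of the trend during the exam, and the expectation that comes from open-label treatment remains.
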